1.2.2.3 Safety profile of everolimus

The following AEs are considered to be class-effects of mTOR inhibitors: stomatitis/oral mucositis/ulcers, infections and infestations, rash and similar events, cytopenia, hemorrhages, non-infectious pneumonitis, hyperglycemia/new-onset diabetes mellitus, renal events, and thromboembolism. The more common metabolic side effects reported with mTOR inhibitors result from inhibitory effects on mTOR-regulated lipid and glucose pathways, while infections stem from the immunosuppressive properties of these agents. Virtually all of the side effects associated with mTOR inhibitors can be managed effectively with dose modification and/or supportive intervention.

The safety profile of everolimus observed in the Phase III BOLERO-2 study is consistent with prior experience in the oncology setting; events are predominantly low grade (grade 1 or 2). An increased risk of non-infectious pneumonitis, infection, and stomatitis in the everolimus plus exemestane arm relative to the control arm [exemestane + placebo] was observed, although each of these events can be effectively managed in this setting.

The most common adverse events (AEs) suspected to be related to treatment, with an incidence $\geq 10\%$, reported in association with everolimus plus exemestane therapy were consistent with what

[figure not shown]
was previously reported: stomatitis, rash, fatigue, decreased appetite, diarrhea, dysgeusia, nausea, pneumonitis, weight loss, anemia, epistaxis, hyperglycemia, thrombocytopenia, and pruritus. The most common grade 3-4 AEs suspected to be related to treatment with an incidence of $\geq 2\%$ were: stomatitis, hyperglycemia, anemia, pneumonitis, fatigue, elevated alanine and aspartate transaminase concentrations, elevated γ -glutamyltransferase concentrations, dyspnea, neutropenia, and thrombocytopenia ([Bachelot et al. 2012](#)). No new safety concerns have emerged compared to previous experience with everolimus monotherapy or combination therapy.

Further details related to everolimus safety can be found in the [[everolimus Investigator's Brochure](#)] and package insert of the local supply of everolimus (if available) for more details.

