3. Its relationship to the ribociclib and/or everolimus treatment (Reasonable possibility that AE is related: No, Yes)
4. Action taken with respect to study or investigational treatment (none, dose adjusted, temporarily interrupted, permanently discontinued, unknown, not applicable)
5. Whether medication or therapy was given (no concomitant medication/non-drug therapy, concomitant medication/non-drug therapy)
6. Whether it is serious, where a serious adverse event (SAE) is defined as in [Section 8.2.1](#)

All adverse events should be treated appropriately. If a concomitant medication or non-drug therapy is given, this action should be recorded.

Once an adverse event is detected, it should be followed until its resolution or until it is judged to be permanent, and assessment should be made at each visit (or more frequently, if necessary) of any changes in severity, the suspected relationship to the ribociclib+everolimus treatment, the interventions required to treat it, and the outcome.

Progression of malignancy (including fatal outcomes), if documented, should not be reported as a serious adverse event.

Events that are clearly consistent with the expected pattern of progression of the underlying disease should not be recorded as AEs. Events that are clearly related to surgical complications experienced as a result of the craniotomy and not related to study participation or the test article(s) should not be recorded as AEs. If there is any indication that the event may be related to study participation or the test article, the event should be recorded as an adverse event.

Adverse events separate from the progression of malignancy (example, deep vein thrombosis at the time of progression or hemoptysis concurrent with finding of disease progression) will be reported as per usual guidelines used for such events with proper attribution regarding relatedness to the drug.

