8.2 Serious adverse events

8.2.1 Definitions

Serious adverse event (SAE) is defined as one of the following:

- Is fatal or life-threatening
- Results in persistent or significant disability/incapacity
- Constitutes a congenital anomaly/birth defect
- Is medically significant, i.e., defined as an event that jeopardizes the patient or may require medical or surgical intervention to prevent one of the outcomes listed above
- Requires inpatient hospitalization or prolongation of existing hospitalization,
- Note that hospitalizations for the following reasons should not be reported as serious adverse events:
 - Routine treatment or monitoring of the studied indication, not associated with any deterioration in condition
 - Elective or pre-planned treatment for a pre-existing condition that is unrelated to the indication under study and has not worsened since signing the informed consent

- Social reasons and respite care in the absence of any deterioration in the patient's general condition
- Hospitalization due solely to progression of the underlying cancer
- Events that are clearly consistent with the expected pattern of progression of the underlying disease should not be recorded as AEs.
- Events that are clearly related to surgical complications experienced as a result of the craniotomy and not related to study participation or the test article(s) should not be recorded as AEs. If there is any indication that the event may be related to study participation or the test article, the event should be recorded as an adverse event.
- Note that treatment on an emergency outpatient basis that does not result in hospital admission and involves an event not fulfilling any of the definitions of a SAE given above is not a serious adverse event

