8.2.2 Reporting

To ensure patient safety, every SAE, regardless of suspected causality, occurring after the first study drug administration and until at least 30 days after the patient has stopped treatment must be reported to Ivy Brain Tumor Center (IBTC) within 24 hours of learning of its occurrence.

Any SAE experienced after this 30 days period should only be reported if the investigator suspects a causal relationship to the treatment. Recurrent episodes, complications, or progression of the initial SAE must be reported as follow-up to the original episode within 24 hours of the investigator receiving the follow-up information. An SAE occurring at a different time interval or otherwise considered completely unrelated to a previously reported one should be reported separately as a new event.

Information about all SAEs is collected and recorded on the Serious Adverse Event Report Form; all applicable sections of the form must be completed in order to provide a clinically thorough report. The investigator must assess and record the relationship of each SAE to each specific study treatment (if there is more than one study treatment), complete the SAE Report Form, and send the completed, signed form [contact] within 24 hours of learning of its occurrence.

The original copy of the SAE Report Form must be kept at the study site.

Follow-up information is sent to the same contact(s) to whom the original SAE Report Form was sent, using a new SAE Report Form stating that this is a follow-up to the previously reported SAE and giving the date of the original report. Each re-occurrence, complication, or progression of the original event should be reported as a follow-up to that event regardless of when it occurs. The follow-up information should describe whether the event has resolved or continues, if and how it was treated, and whether the patient continued or withdrew from study participation.

If the SAE is not previously documented in the Investigator's Brochure or Package Insert (new occurrence) and is thought to be related to the treatment, IBTC may need to report the event in a MedWatch report to the FDA.

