8.6 Data and Safety Monitoring Board

A group of experts will be assembled to assess the progress, safety data and, if needed critical efficacy endpoints of the study as part of a Data and Safety Monitoring Board. Safety and toxicity will be assessed throughout the study duration, including preoperative and peri-operative time periods. The DSMB charter will be documented in a separate document. Study stopping rules are, if two or more patients have a \geq 4 week delay to surgery due to ribociclib or everolimus related toxicity, the study will be stopped. Also see Table 8 for additional stopping rules. Based on its

review, the DSMB will provide recommendations regarding study modification, continuation or termination.

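### Craniotomy complications judged purely surgical are kept off the AE record, so drug-related peri-operative bleeding, infection and clots may be under-recorded by an amount nobody can measure

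*Combined protocol and SAP*

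**What the plan says.** Section 8.1.1 sets two joint conditions for leaving an event off the record. It must belong to "Events that are clearly related to surgical complications experienced as a result of the craniotomy" and must also be unrelated to the study: "and not related to study participation or the test article(s) should not be recorded as AEs". A safeguard follows: "If there is any indication that the event may be related to study participation or the test article, the event should be recorded as an" AE. Section 8.2.1 repeats the exclusion under the SAE definition: "Events that are clearly related to surgical complications experienced as a result of the craniotomy and not related to study participation".

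Other sections bear on this:

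- **1.2.2.3** lists as mTOR-inhibitor class effects "infections and infestations, rash and similar events, cytopenia, hemorrhages, non-infectious pneumonitis", and, later in the same list, thromboembolism.
- **4.1.1** places the last dose 1 to 3, 7 to 9 or 23 to 25 hours before craniotomy.
- **6.4.3** states that the study is open-label.
- **8.2.2** requires reporting of "every SAE, regardless of suspected causality, occurring after the first study drug administration", until at least 30 days after treatment stops.
- **8.6** says: "Safety and toxicity will be assessed throughout the study duration, including preoperative and peri-operative time periods".
- **8.6.1** builds the escalation report from cohorts, dose levels, adverse events, safety reports and DLTs.

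**The concern.** The exclusion puts the causality judgement before the recording. The site knows that the patient took both drugs, decides case by case, and has no criteria for when an event is clearly surgical. One post-operative bleed, infection or clot seldom shows whether the drug contributed. A drug effect would appear mainly as a higher frequency, and a frequency needs every event in the count.

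An added peri-operative risk is a natural safety question for a trial that doses patients just before brain surgery. If events are removed by attribution before they are written down, the AE tables and the DSMB reports may run low, and the shortfall cannot be reconstructed from the AE record afterwards.

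**Working it through.** The plan states no figure on this point, so there is none to reproduce. The check sets the sections side by side and then adds an illustration.

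**1. Does the safeguard sentence close the gap?** Only in part. It requires recording on any indication of relatedness. It does not say whether appearing in the 1.2.2.3 list, hours after a dose, is an indication. One site could record every post-operative hemorrhage and another none, and both could claim to follow the text.

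**2. Is the exclusion consistent with the rest of Section 8?**
- 8.2.1 removes serious events on causal grounds, while 8.2.2 wants them whatever the suspected cause.
- 8.1.1 already has a Yes/No relatedness item for each AE, so attribution can be recorded without excluding anything.
- For a thrombosis that coincides with progression, 8.1.1 says to report it and then attribute it. Events around the craniotomy are handled the other way round.

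**3. Is there another formal route?**
- The special-interest list (8.1.3) covers hepatotoxicity, QT prolongation, interstitial lung disease and pneumonitis. It omits bleeding, infection and clots.
- The stopping rule worded in 8.6 concerns delay to surgery and does not cover complications after it.
- The Phase 0 DLT window is the first 5 days (6.1.3). Surgery is on Day 5 for cohorts 1 and 2 and on Day 6 for cohort 3 (7.1.1.11.4), so most post-operative events fall outside it.

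The general AE record is therefore the main place where these events would appear.

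**4. Illustration of size.** The total n = 30 is from 9.7.1. The background rate p0, the true rate p1 and the unrecorded share f are assumptions; the documents give none of them. The recorded count is X ~ Binomial(30, p1 × (1 − f)). A rise is flagged if X ≥ r, where r is the smallest value with P(X ≥ r | p0) ≤ 0.10.

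- For p0 = 5%, r = 4, and P(X ≥ 4 | 5%) = 6.1%.
- For p0 = 10%, r = 6, and P(X ≥ 6 | 10%) = 7.3%.

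| p0 → p1 | Expected events, full record | Chance of flag, f = 0 | f = 25% | f = 50% |
|---|---|---|---|---|
| 5% → 10% | 30 × 0.10 = 3.0 | 35% | 18% | 6% |
| 5% → 15% | 30 × 0.15 = 4.5 | 68% | 44% | 18% |
| 10% → 20% | 30 × 0.20 = 6.0 | 57% | 29% | 7% |
| 10% → 30% | 30 × 0.30 = 9.0 | 92% | 70% | 29% |

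When half the events are lost, a doubled rate is recorded at its background value (0.20 × 0.5 = 0.10), so the chance of a flag equals the false-alarm rate. The comparison is with an external rate that is itself fully recorded.

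**5. Single dose levels.** With 3 patients, the chance of at least one event is 1 − 0.9³ = 27% at a 10% rate and 1 − 0.8³ = 49% at 20%. A single level says little, so an overall table is needed as well.

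**The case against.** The strongest reply is that the text, read strictly, already protects these events. Both conditions must hold. An event that cannot be told apart from a drug effect is not clearly surgical, and a listed class effect hours after dosing is arguably an indication of relatedness. This stands as one fair reading, but the protocol does not say that it is the intended one.

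Other capture exists. Section 6.3 and Table 13 record medications, surgeries and procedures, so re-operation, antibiotics or anticoagulation would leave a trace. Deaths are collected, and post-operative blood counts, chemistry, examination and MRI are scheduled. If 8.2.2 prevails over 8.2.1, serious complications are reported. For these reasons a reader who infers that a drug-caused excess could not be seen at all goes further than the documents allow. These traces are not graded AEs with a relatedness call, however, and 8.6.1 does not name them as content of the escalation report.

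Sections 8.2.1 and 8.2.2 can also be read in sequence: first the definition, then reporting of what remains. That is possible, but the wording does not say so. Section 8.6 does not contradict the exclusion; it states an intention that a filtered record serves poorly. The DSMB charter is a separate document and may ask for more.

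The point about comparison also stands. There is no untreated surgical group, and even a full record detects a doubling only 35% to 57% of the time in the illustration. If filtering took the same share at every dose level, the ratio between levels would survive, though on fewer events and with that share unknown.

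Two further inferences fail. A reader might expect the loss to be worst at Levels 4 to 6 because everolimus is given on Day 5, but Levels 0 to 3 also include a Day 5 dose. A reader might also expect the MTD to be distorted, but most post-operative events lie outside the Phase 0 DLT window whether or not they are recorded.

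**Conclusion.** The concern holds in a limited form. Sections 8.1.1 and 8.2.1 allow peri-operative events to be left unrecorded on a prior, unblinded causality judgement without criteria, for event types that the protocol itself lists as class effects. Under-recording is possible and its extent cannot be measured from the AE record. The documents do not show that events are in fact being lost. They do show that 8.2.1 and 8.2.2 need to be reconciled.

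The size is illustrative only. Under assumed background rates of 5% or 10% and a doubling, losing half the events cuts the chance of a flag from 35% to 6%, or from 57% to 7%. With about 30 patients, no untreated surgical group and no background rate in the documents, even complete data would be descriptive, and any comparison would need an external rate. What is at stake is the completeness of the peri-operative safety description and of the DSMB's information. This is a worthwhile and inexpensive improvement.

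**What to change.** - In 8.1.1 and 8.2.1, remove the exclusion for surgical complications. Record every event from first dose to 30 days after last dose, which is the AE period already in Table 13.
- Extend the relatedness item in 8.1.1 to an attribution field: drug, surgery, both, or tumour. The separate rule on disease progression is not at issue here.
- Reconcile 8.2.1 with 8.2.2, so that it is plain which serious post-operative events are reported.
- In 8.6.1, have each DSMB report list or tabulate post-craniotomy hemorrhage, infection, wound and thromboembolic events by dose level and overall, labelled as descriptive. If a comparison is wanted, name the external rate and its source in advance.

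The cost is more AE forms and longer listings, some of them purely surgical. No visit, test or treatment rule changes.

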8.1.2 Laboratory test abnormalities

8.1.2.1 Definitions and reporting

Laboratory abnormalities that constitute an Adverse event in their own right (are considered clinically significant, induce clinical signs or symptoms, require concomitant therapy or require changes in ribociclib and/or everolimus treatment), should be recorded. Whenever possible, a diagnosis, rather than a symptom should be provided (e.g. anemia instead of low hemoglobin). Laboratory abnormalities that meet the criteria for Adverse Events should be followed until they have returned to normal or an adequate explanation of the abnormality is found. When an abnormal laboratory or test result corresponds to a sign/symptom of an already reported adverse event, it is not necessary to separately record the lab/test result as an additional event.

Laboratory abnormalities, that do not meet the definition of an adverse event, should not be reported as adverse events. A Grade 3 or 4 event (severe) as per CTCAE does not automatically indicate a SAE unless it meets the definition of serious as defined below and/or as per investigator's discretion. A dose hold or medication for the lab abnormality may be required by the protocol in which case the lab abnormality would still, by definition, be an adverse event and must be reported as such.

8.1.3 Adverse events of special interest (AESI)

Based upon the currently available information from the pre-clinical studies, mechanism of action, pharmacological class effect, and clinical data for ribociclib and everolimus, defined AESIs to date are: Hepatotoxicity, QT prolongation and Interstitial Lung Disease, and Pneumonitis.

8.2 Serious adverse events

8.2.1 Definitions

Serious adverse event (SAE) is defined as one of the following:

- Is fatal or life-threatening
- Results in persistent or significant disability/incapacity
- Constitutes a congenital anomaly/birth defect
- Is medically significant, i.e., defined as an event that jeopardizes the patient or may require medical or surgical intervention to prevent one of the outcomes listed above
- Requires inpatient hospitalization or prolongation of existing hospitalization,
- Note that hospitalizations for the following reasons should not be reported as serious adverse events:
 - Routine treatment or monitoring of the studied indication, not associated with any deterioration in condition
 - Elective or pre-planned treatment for a pre-existing condition that is unrelated to the indication under study and has not worsened since signing the informed consent

- Social reasons and respite care in the absence of any deterioration in the patient's general condition
- Hospitalization due solely to progression of the underlying cancer
- Events that are clearly consistent with the expected pattern of progression of the underlying disease should not be recorded as AEs.
- Events that are clearly related to surgical complications experienced as a result of the craniotomy and not related to study participation or the test article(s) should not be recorded as AEs. If there is any indication that the event may be related to study participation or the test article, the event should be recorded as an adverse event.
- Note that treatment on an emergency outpatient basis that does not result in hospital admission and involves an event not fulfilling any of the definitions of a SAE given above is not a serious adverse event

8.2.2 Reporting

To ensure patient safety, every SAE, regardless of suspected causality, occurring after the first study drug administration and until at least 30 days after the patient has stopped treatment must be reported to Ivy Brain Tumor Center (IBTC) within 24 hours of learning of its occurrence.

Any SAE experienced after this 30 days period should only be reported if the investigator suspects a causal relationship to the treatment. Recurrent episodes, complications, or progression of the initial SAE must be reported as follow-up to the original episode within 24 hours of the investigator receiving the follow-up information. An SAE occurring at a different time interval or otherwise considered completely unrelated to a previously reported one should be reported separately as a new event.

Information about all SAEs is collected and recorded on the Serious Adverse Event Report Form; all applicable sections of the form must be completed in order to provide a clinically thorough report. The investigator must assess and record the relationship of each SAE to each specific study treatment (if there is more than one study treatment), complete the SAE Report Form, and send the completed, signed form [contact] within 24 hours of learning of its occurrence.

The original copy of the SAE Report Form must be kept at the study site.

Follow-up information is sent to the same contact(s) to whom the original SAE Report Form was sent, using a new SAE Report Form stating that this is a follow-up to the previously reported SAE and giving the date of the original report. Each re-occurrence, complication, or progression of the original event should be reported as a follow-up to that event regardless of when it occurs. The follow-up information should describe whether the event has resolved or continues, if and how it was treated, and whether the patient continued or withdrew from study participation.

If the SAE is not previously documented in the Investigator's Brochure or Package Insert (new occurrence) and is thought to be related to the treatment, IBTC may need to report the event in a MedWatch report to the FDA.

8.3 Emergency unblinding of treatment assignment

N/A

8.4 Pregnancies

To ensure patient safety, each pregnancy occurring while the patient is on study treatment must be reported to IBTC immediately (within 24 hours) of learning of its occurrence. Patients who become pregnant during the trial must be withdrawn. The pregnancy will be followed up from the estimated date of delivery plus 3 months to determine outcome, including spontaneous or voluntary termination, details of the birth, and the presence or absence of any birth defects, congenital abnormalities, or maternal and/or newborn complications.

Women of childbearing potential should be advised to use highly effective contraception methods while they are receiving study treatment and up to 3 months after treatment has been stopped.

If a pregnancy occurs while on ribociclib treatment, the newborn will be followed for at least 3 months.

